7.3 PROCEDURE FOR WITHDRAWAL OF PATIENTS FROM STUDY FOLLOW-UP SCHEDULE

Participants, who meet the study criteria, consent to participation, and complete the intake interview will be considered enrolled. Every effort will be made by the OTIS Research Center Staff to complete all study visits as scheduled, and to collect outcome interview, medical records, and physical examination data. Subjects who do not complete the outcome interview following the end of the pregnancy will be considered lost to follow-up. Multiple attempts will be made to contact participants by telephone, mail, email, up to 1 year past the expected due date before a subject is deemed lost. Subjects who decline to complete participation after enrollment will be considered to have withdrawn consent and information collected on reasons for withdrawal. The statistical analysis plan will specify how these patients for whom outcome information is not available for study endpoints will be considered.

7.4 LOGISTIC ASPECTS

[figure not shown]
The OTIS Research Center maintains a national (U.S. and Canada) toll-free number, staffs this number during business hours, and is set up to take telephone messages after business hours. Participating OTIS referral sites screen for potential study candidates and obtain permission to refer to the OTIS Study Center. In addition, women may learn about the study through their health care provider, the web, or other media and promotional activities. Health care providers can learn about the study at Scientific Meetings where OTIS exhibits and/or presents information. The website describes the OTIS organization, the study objectives, and provides multiple modalities through which potential participants or health care providers can contact the OTIS Research Center to obtain more information. In all cases, however, once

CSD-003149 VERSION N°1.0 (20-JUL-2010)

Ensure that the printed copy of this document is the current version available on the Intranet.

screened, an eligible participant is the woman herself, and she is the person who must provide informed consent.

Figure 1: Study flow diagram

8 STATISTICAL METHODOLOGY

This section provides specifications for preparation of final statistical analysis plan (SAP), which will be issued prior to final database lock at the end of the study. Any differences compared to this statistical section should be identified and documented in final SAP. All interim annual study reports as described in Section 9 will provide descriptive data only. Statistical analysis will not be performed until the cohort study has been completed. Additional data on exposed pregnancies that do not qualify for the cohort study, as described in Section 10.5, will be included in interim and final reports using descriptive statistics only.

8.1 ANALYSIS POPULATION

This study consists of 3 cohorts recruited from the United States and Canada. The exposed group (Cohort I) consists of pregnant women with a confirmed diagnosis of MS and

teriflunomide exposure at anytime from the 1st day of LMP up to and including the 12th week after the first day of the LMP. The diseased comparison group (Cohort II) consists of pregnant women with a confirmed diagnosis of MS who have not been exposed to teriflunomide during the current pregnancy. The healthy comparison group (Cohort III) consists of pregnant women who do not have MS and have no known exposure to any known teratogen or teriflunomide. Participants who are deemed lost-to-follow-up or who withdraw before the known outcome of pregnancy (Section 7.3) will be reported in descriptive tables in all interim and final reports, but will be excluded from statistical comparisons.

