6.2.1 Inclusion criteria for the cohort study

Cohort I: Teriflunomide-exposed pregnant women with MS

- Pregnant women who have previously been treated with teriflunomide, including women who were treated during a clinical trial, who are participating in another registry, or who are treated with other approved disease modifying therapy for MS, for any number of days, at any dose, and at anytime from the 1st day of the last menstrual period up to and including the 12th week after the first day of the LMP.
- Pregnant women who have provided an oral and/or written consent to enroll no later than 20 completed weeks from LMP.
- Pregnant women who agree to the conditions and requirements of the study including the interview schedule, release of medical records, and the physical examination of live born infants (up to 1 year post birth).

Cohort II – Pregnant women with MS not exposed to teriflunomide during the current pregnancy

- Pregnant women with a diagnosis of MS who have:
 1. Not taken teriflunomide at any time but who may or may not have taken another medication for MS during the current pregnancy, **or**
 2. Previously been treated with teriflunomide within 2 years prior to the index pregnancy and have documented blood levels below 0.02 mcg/mL prior to pregnancy, **or**
 3. Previously been treated with teriflunomide greater than 2 years prior to the index pregnancy
- Pregnant women who have provided oral and/or written consent to enroll no later than 20 completed weeks from LMP.
- Pregnant women who agree to the conditions and requirements of the study including the interview schedule, release of medical records, and the physical examination of live born infants (up to 1 year post birth)
- Pregnant women can be taking any other approved disease modifying therapy for MS

Cohort III - Pregnant women without MS and no exposure to any known human teratogen

- Pregnant women who do not have a known diagnosis of MS and have no known exposure to a known human teratogen, as determined by the referring Teratogen Information Specialists and confirmed by the OTIS Research Center.
- Pregnant women who have provided oral and/or written consent to enroll no later than 20 completed weeks from LMP.
- Pregnant women who agree to the conditions and requirements of the study including the interview schedule, release of medical records, and the physical examination of live born infants (up to 1 year post birth).

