6.2.2 Exclusion criteria for Cohort Study

Cohort I: Teriflunomide-exposed pregnant women with MS

- Pregnant women with exposure to teriflunomide commencing after the 12th week post-LMP.
- Pregnant women who come in first contact with the project after prenatal diagnosis of a major structural defect.
- Pregnant women who first come in contact with the project after 20 completed weeks' gestation.

- Pregnant women who had previously enrolled in the study for a previous pregnancy (only 1 pregnancy, per woman, may be registered).
- Retrospectively reported cases.

Cohort II: Pregnant women with MS not exposed to teriflunomide during the current pregnancy

- Pregnant women who come in first contact with the project after prenatal diagnosis of a major structural defect.
- Pregnant women who first come in contact with the project after 20 completed weeks' gestation.
- Pregnant women who had previously enrolled in the study for a previous pregnancy (only 1 pregnancy, per woman, may be registered).
- Retrospectively reported cases.
- Pregnant women who had previously been treated with teriflunomide if they had received any dose of the drug within 2 years prior to the index pregnancy and do not have documented blood levels below 0.02 mcg/mL prior to pregnancy.

Cohort III: Pregnant women without MS and no exposure to any known human teratogen

- Pregnant women who first come in contact with the project after 20 completed weeks' gestation.
- Pregnant women who first come in contact with the project after prenatal diagnosis of a major structural defect.
- Pregnant women who had previously enrolled in the study for a previous pregnancy (only 1 pregnancy, per woman, may be registered).
- Retrospectively reported cases.

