8.2 ANALYSIS VARIABLES

The primary analysis variable is proportion of live born infants with a major structural birth defect within the first year of life and the secondary analysis variables: proportion of major structural defects in all pregnancies, proportion of infants with a pattern of 3 or more specific minor anomalies, the incidence of spontaneous abortion; stillbirth; preterm delivery; small-for-gestational age on birth weight, length, head circumference; small for age at 1 year follow-up on weight, length or head circumference.

Additional analysis variables that may or may not be included as important confounders or in sub-analyses include but are not limited to the following:

- Maternal age
- Maternal race/ethnicity
- Socioeconomic status
- Prior pregnancy history: gravidity/parity and previous outcomes
- Periconceptional use of folic acid containing supplements
- Unintended pregnancy
- Gestational age at enrollment
- Exposure to other medications (including known teratogens) and other MS medications
- Comorbidities
- Disease severity measure (s)
- Dose and gestational timing of exposure to teriflunomide
- Gestational timing and course of cholestyramine elimination
- Blood levels of teriflunomide if performed in pregnancy

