8.3 STATISTICAL METHODS

8.3.1 Primary endpoint

The primary endpoint is rate of major structural defects in live born infants. Due to the expected low incidences of major defects, diagnosed within the first year of life, the primary comparison will be carried out using Fisher's exact test between the teriflunomide-exposed group (Cohort I) and the disease-matched comparison group (Cohort II). Although Cohort II is "matched" to Cohort I on the underlying maternal diagnosis of MS, no a priori matching on disease severity is performed at the time of recruitment. Therefore, measures of MS severity will be addressed as confounders in the analyses comparing Cohort I to Cohort II as described below.

Due to the observational nature of the study, it is necessary to adjust for confounders to address baseline differences between the teriflunomide exposed and the comparison groups.

Ensure that the printed copy of this document is the current version available on the Intranet.

The potential confounders to be evaluated will be those itemized in the analysis variables in [Section 8.2](#) (e.g., maternal age, MS severity). Confounders will be those variables that modify the odds ratio for the outcome by at least 10% in logistic regression with exposure to teriflunomide and the potential confounder as predictors. In addition, any variable that is deemed to be clinically relevant will be considered for inclusion in multivariate analysis even if the 10% criterion is not met. The adjustment for confounders will be carried out using logistic regression, the primary outcome variable as the dependent variable, and with confounders included in the models as independent variables adjusting for the effect of exposure. Stepwise procedures will be used in case of many identified confounders, as sample size permits. Propensity scoring methods will be considered. The analysis of major birth defects will be further stratified based on prenatal diagnosis performed prior to enrollment or not.

Secondary comparisons will be made between the teriflunomide exposed group (Cohort I) and the healthy comparison group (Cohort III). The rate of major structural defects will also be compared to the most recently available rate from the MACDP.

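### Known-teratogen exposure is barred only in Cohort III, so the secondary Cohort I versus Cohort III comparison is tilted towards an apparent teriflunomide excess

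*Protocol*

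**What the plan says.** Section 6.2.1 admits women to Cohort III only if they "have no known exposure to a known human teratogen, as determined by the referring Teratogen Information Specialists", with confirmation by the research center. Section 8.1 carries this into the analysis population, describing Cohort III as "pregnant women who do not have MS and have no known exposure to any known teratogen or teriflunomide".

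The criteria for the other two cohorts contain nothing equivalent. In Cohort I the only exclusion based on a drug exposure concerns the timing of teriflunomide itself: "Pregnant women with exposure to teriflunomide commencing after the 12th week post-LMP". For Cohort II the restriction concerns past teriflunomide only, and section 6.2.1 adds "Pregnant women can be taking any other approved disease modifying therapy for MS".

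On the analysis side, section 8.3.1 makes Cohort I versus Cohort II the primary comparison, by an unadjusted Fisher's exact test, and then states "Secondary comparisons will be made between the teriflunomide exposed group (Cohort I) and the healthy comparison group (Cohort III". Section 8.2 lists "Exposure to other medications (including known teratogens) and other MS medications" under the heading "Additional analysis variables that may or may not be included as important confounders", or in sub-analyses. Section 8.3.1 gives the entry rule: "Confounders will be those variables that modify the odds ratio for the outcome by at least 10% in logistic regression". Variables judged clinically relevant may also be considered, and propensity methods are mentioned as a possibility.

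**The concern.** A comparison of exposed and unexposed pregnancies should apply the same restriction on other causes of the outcome to both sides. Here the restriction applies only to the healthy cohort. Apart from exposures that go unrecognized or arise after enrollment, other-teratogen exposure can sit only on the Cohort I side. A defect caused by such an exposure would then count towards teriflunomide in the Cohort I versus III contrast, so the bias has one direction.

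Section 3.1 says that controlling for other exposures is critical when a medication exposure is studied. Section 8 turns this into an optional covariate. For Cohort I versus III, the covariate would also be absent from one arm by design.

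**Working it through.** **Inputs from the protocol (section 8.4).** Enrollment is 75 in Cohort I and 125 in each comparison cohort, with a live-birth yield of 85%, a baseline major-defect rate of 3%, two-sided alpha of 0.05 and a detectable relative risk of 5.57.

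**The plan's own figures.**
- Live births: 75 × 0.85 = 63.75 and 125 × 0.85 = 106.25, matching the stated 64 and 106.
- Detectable effect: the exposed rate is 0.03 × 5.57 = 16.71%. Enumerating both binomials (64 and 106), Fisher's test at 0.025 in the upper tail has power 80.9%. The two-sided version that sums all tables no more likely than the observed one has power 84.5%. The stated 5.57 is therefore sound, and this point does not affect it.

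**Expected events with no effect.** 64 × 0.03 = 1.9 and 106 × 0.03 = 3.2, about 5 in total.

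**Bias in Cohort I versus III.** The protocol gives neither the share s of Cohort I exposed to another known teratogen nor the defect rate r in those women. I assume s = 2%, 5% or 10% and r = 10% or 20%, with teriflunomide itself having no effect:

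Cohort I rate = 0.03(1 − s) + r·s; risk ratio = rate / 0.03; excess cases = 64 × (rate − 0.03).

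| s | r | Cohort I rate | Risk ratio | Excess cases in 64 | Two-sided Fisher rejection |
|---|---|---|---|---|---|
| 2% | 10% | 3.14% | 1.05 | 0.09 | 1.9% |
| 2% | 20% | 3.34% | 1.11 | 0.22 | 2.2% |
| 5% | 10% | 3.35% | 1.12 | 0.22 | 2.2% |
| 5% | 20% | 3.85% | 1.28 | 0.54 | 3.1% |
| 10% | 10% | 3.70% | 1.23 | 0.45 | 2.8% |
| 10% | 20% | 4.70% | 1.57 | 1.09 | 5.4% |

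The last column is the exact probability of a significant result with 64 versus 106 live births. With no bias it is 1.8%. Five of the six scenarios add less than one expected case.

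**Whether the adjustment route closes the gap.** In the lowest scenario the ratio moves by about 5%, below the 10% screen, and the next two only just reach 10%. About 5 events also make the screen itself unstable. Because Cohort III has no teratogen-exposed women by design, there is no overlap on this variable, and propensity methods cannot balance it. A logistic model with cohort and a teratogen indicator takes its cohort effect from the unexposed part of Cohort I against Cohort III. That is the restricted comparison, so specifying the restriction in advance does what a valid adjustment would do.

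**Cohort I versus II.** Write q1 and q2 for the co-exposed shares and k for the relative risk of the other teratogen. The risk ratio is [1 + q1(k − 1)] / [1 + q2(k − 1)].
- q1 = q2: 1.00 for any k.
- q1 = 10%, q2 = 5%: 1.10/1.05 = 1.05 at k = 2, and 1.40/1.20 = 1.17 at k = 5.
- q1 = 5%, q2 = 10%: 1.05/1.10 = 0.95 at k = 2, and 1.20/1.40 = 0.86 at k = 5.

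No direction is built in.

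**Sensitivity to single cases (two-sided Fisher).** 4/64 v 3/106 gives p = 0.43; 7/64 v 3/106 gives p = 0.042. Removing one co-exposed case from the latter (6/63 v 3/106) gives p = 0.080.

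**The case against.** The strongest reply is that the protocol already deals with this. Known-teratogen exposure is named in section 8.2 as a candidate confounder or sub-analysis variable. Section 8.3.1 gives a 10% screen, a route for clinically relevant variables that fail the screen, and possible propensity methods. Section 8 calls itself the specification for a later SAP, where sensitivity analyses usually belong. Cohort III is only the secondary comparator and can be seen as a deliberate low-risk reference.

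Much of this stands. The adjustment route exists and the comparison is secondary. What does not stand is that the matter is mere missing detail. The one-sided restriction is a stated rule, and the protocol commits to comparing the cohorts as so defined. None of the listed routes guarantees that the exposure is handled.

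A reader might infer three stronger things that the protocol does not support.
- That teratogen exposure in Cohort I versus II is uncontrolled. Both cohorts follow the same rule, no difference is built in, and an adjustment route is named. Control there is optional and weak, which is a smaller complaint.
- That the protocol expects teratogen use in Cohorts I and II. Section 8.2 is a list of possible covariates and gives no frequency. The sentence allowing other MS therapy in Cohort II does not say that any such therapy is a known human teratogen.
- That one or two cases would decide the result. Two extra cases on the null expectation, roughly 2/64 v 3/106, leave p = 0.43. A single case matters only when the count is already near 7/64.

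**Conclusion.** The point holds for the secondary comparison. Cohort I versus Cohort III is asymmetric by design and biased towards an apparent teriflunomide excess if any Cohort I woman took another known teratogen. The size is unknown. Under the assumed 2% to 10% co-exposure and 10% to 20% defect rate, the null risk ratio is 1.05 to 1.57. Those inputs are assumptions, and the upper end needs a co-exposed defect rate of 0.20/0.03 = 6.7 times background. Even then the bias is far below the detectable 5.57, and false-positive rejection reaches 5.4% at most.

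For the primary comparison, the conclusion is limited to optional control with few events to support it. The sample size and the primary test are unaffected.

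**What to change.** Leave enrollment as it is and add two sentences to section 8.3.1:

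1. Cohort I versus Cohort III is analyzed after excluding Cohort I pregnancies exposed to a known human teratogen other than teriflunomide, using the same determination that section 6.2.1 applies to Cohort III. This may be the main version of the comparison or stand alongside the full-cohort result.
2. A sensitivity analysis of Cohort I versus Cohort II applies the same exclusion to both cohorts.

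The medication and exposure data are already collected under section 7.2, so no new procedure is needed. The cost is the loss of a few pregnancies from these analyses, mainly from the small Cohort I, and slightly lower precision.

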7.2 DATA COLLECTED FROM THE MOTHER

Following oral administration of informed consent, a structured maternal intake telephone interview will be conducted by a trained Research Associate at OTIS. This interview will include questions as itemized below and information will be updated at all subsequent maternal interviews. Women who have had teriflunomide exposure will be informed that teriflunomide serum levels and elimination procedures can be arranged through their health care provider and/or the teriflunomide patient management program.

Following the initial intake interview, participants will be sent a pregnancy diary on which they will be asked to record any additional exposures or events as the pregnancy progresses. Women who have enrolled in the study prior to 16 weeks post-LMP will be interviewed by telephone at 20-22 weeks post-LMP, 32-34 weeks post-LMP and within 6 weeks after the expected due date. Women who have enrolled between 16 and 20 weeks post-LMP will be interviewed at 32-34 weeks post-LMP and within 6 weeks after expected due date (see

OSD-003149 VERSION N°1.0 (20-JUL-2010)

Ensure that the printed copy of this document is the current version available on the Intranet.

Table 2). The purpose of these interviews will be to update records of pregnancy exposures and results of prenatal tests, to remind women to maintain the exposure diary, to update phone number and address information, and to determine if the pregnancy has ended prior to the expected due date. The maternal outcome interview will be conducted within approximately 4 weeks of the end of the pregnancy.

Data collected from these interviews and the diary includes the following:

During Pregnancy:

- History of previous pregnancy outcomes
- Health and family medical history including history of MS disease
- Socioeconomic and demographic information including occupation, education, race/ethnicity of mother and father, and family income category
- Course of current pregnancy including prenatal tests, test results, pre-pregnancy body mass index
- Exposures during the current pregnancy including over-the-counter and prescription medications including all treatments for MS, vitamin supplements, herbal products, tobacco, alcohol, illicit drugs, occupational and environmental exposures
- Dosage and dates of teriflunomide
- Cholestyramine or charcoal elimination procedure(s), dates and compliance
- If blood levels for teriflunomide were measured, dates and results

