8.3.2 Secondary endpoints

The secondary endpoints of this study include: proportion of major structural defects in all pregnancies excluding lost-to-follow-up, prevalence of a specific pattern of 3 or more minor structural defects in the live born infants who receive the dysmorphological examination, rates of spontaneous abortion, preterm delivery, proportion of live born infants who are small for gestational age (less than or equal to 10th percentile for gestational age and sex) on weight, length or head circumference, and proportion of infants less than or equal to the 10th percentile for sex and age on weight, length or head circumference at 1 year postnatal evaluation. The above endpoints, other than spontaneous abortion and preterm delivery, are binary and will be analyzed in the same fashion as major structural defects, with the exception that the Chi-squared test will be used for comparison between the exposed and the comparison group when the events are not rare. For spontaneous abortion and preterm delivery, survival analyses incorporating left truncation for spontaneous abortion (women may enroll in the study any time between 0 to 20 weeks of gestational age) and right censoring when the subject is no longer at risk of the event are conducted. The comparison between the exposed and the comparison group will be carried out using log-rank test, and confounders will be adjusted using the Cox proportional hazards regression model.

For all endpoints, exposure effect will also be investigated using the timing and dose of exposure, in a fashion similar to using the group indicator as above.

Also influencing fetal exposure is the success of the cholestyramine elimination procedure. Therefore, detailed data on the dose, gestational timing of the elimination procedure (s) and adherence to the guidelines for drug elimination procedure will be incorporated into the analysis of exposure in relation to outcome, and these maternally collected data will be supplemented by medical records and blood levels as available.

CSD-003149 VERSION N°1.0 (20-JUL-2010)

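### Section 8.1 excludes lost and early-withdrawn women from all comparisons, including the two survival endpoints where their known event-free time could be kept and censored (low severity)

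*Protocol*

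**What the plan says.** Section 8.1 covers this group: "Participants who are deemed lost-to-follow-up or who withdraw before the known outcome of pregnancy". They "will be reported in descriptive tables in all interim and final reports, but will be excluded from statistical comparisons". The rule names no endpoint and has no exception.

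Section 7.3 defines loss by one missing contact: "Subjects who do not complete the outcome interview following the end of the pregnancy will be considered lost to follow-up". Interviews completed earlier do not change that status. The same section then defers the handling: "The statistical analysis plan will specify how these patients for whom outcome information is not available for study endpoints will be considered". The opening of section 8 makes that section the specification for the SAP and asks that departures from it be documented.

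For the two endpoints at issue, 8.3.2 reads: "For spontaneous abortion and preterm delivery, survival analyses incorporating left truncation for spontaneous abortion", with "right censoring when the subject is no longer at risk of the event are conducted". It continues: "The comparison between the exposed and the comparison group will be carried out using log-rank test", with Cox regression for adjustment.

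Event-free time is collected on the way. Section 7.2 states: "Women who have enrolled in the study prior to 16 weeks post-LMP will be interviewed by telephone at 20-22 weeks post-LMP", and again at 32-34 weeks; women enrolled at 16 to 20 weeks have the 32-34 week interview. One stated purpose of these calls is to learn whether the pregnancy has ended. Table 2 shows somewhat different windows (16-20 and 26-32 weeks), but either schedule includes a contact well past week 20.

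**The concern.** Section 7.2.3.4 defines spontaneous abortion as a loss before 20 completed weeks. A woman who is still pregnant at 21 or 33 weeks has passed that whole risk period without the event. If she then misses the outcome interview, 8.1 removes her from the spontaneous-abortion comparison because of something that happened after the risk period ended. For preterm delivery, the weeks in which she was known to be pregnant are discarded too.

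The deletion is one-sided. Among women whose status at 20 weeks is known, those removed for later loss are all event-free, so each cohort's event rate rises a little. If loss is the same in both cohorts, the inflation cancels in the hazard ratio. If one cohort loses more women, its risk looks too high. Section 3.2.1 expects virtually all teriflunomide exposures to occur in unintended pregnancies, with resulting differences in age, race and other factors. Equal retention is therefore not guaranteed, though the protocol gives no figure for a difference. Log-rank and Cox methods can use this partial follow-up, and the plan already uses left truncation to treat late entry properly.

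**Working it through.** **1. The plan's own figure.** Inputs from section 8.4 and Table 3: 75 exposed and 125 comparison women, baseline spontaneous-abortion rate 10%, relative risk 2.55, chi-square test, two-sided 0.05, 80% power. So p0 = 0.10 and p1 = 0.255.

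Power = Φ[(p1 − p0 − 1.96·SE0)/SE1], where SE0 uses the pooled proportion and SE1 the separate ones.

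- Pooled proportion = (75×0.255 + 125×0.10)/200 = 0.1581
- SE0 = 0.0533 and SE1 = 0.0570
- z = (0.155 − 1.96×0.0533)/0.0570 = 0.886, so power = 0.812

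The stated 2.55 reproduces to within two points of 80% power. Solving for exactly 80% gives a relative risk of 2.52.

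**2. The same figure under the 8.1 exclusion.** Section 8.4 expects 4% loss: 0.04×75 = 3 and 0.04×125 = 5 women, leaving 72:120. Then SE0 = 0.0544, SE1 = 0.0582, z = 0.831 and power = 0.797; the detectable relative risk is 2.56. The cost is about 1.5 points of power.

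**3. Effect on the spontaneous-abortion hazard ratio when the true value is 1.00.** Entry is at 7.5 weeks (middle of the 6-9 week mean in 8.4), so the risk period is T = 20 − 7.5 = 12.5 weeks. With 10% risk, the event hazard is h = −ln(0.9)/12.5 = 0.00843 per week. Assumptions: loss is independent of outcome, contact is continuous, and loss is spread from entry to week 40, so W = 32.5 weeks. For total loss l, the loss hazard is c = −ln(1−l)/W and s = h + c. When lost women are dropped:

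- events kept: E = (h/s)(1 − e^(−sT))
- event-free women kept: F = 0.9(1−l)
- time of the women with events: A = h[(1 − e^(−sT))/s² − T·e^(−sT)/s]
- estimated rate = E/(A + F·T)

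| Loss l | E | F | A | Rate per week |
|---|---|---|---|---|
| 4% | 0.09923 | 0.864 | 0.6077 | 0.008699 |
| 5% | 0.09904 | 0.855 | 0.6061 | 0.008769 |
| 8% | 0.09844 | 0.828 | 0.6012 | 0.008989 |
| 12% | 0.09762 | 0.792 | 0.5944 | 0.009302 |
| 15% | 0.09699 | 0.765 | 0.5892 | 0.009554 |

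Hazard ratios under exclusion:

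- 4% v 4%: 1.00 (each rate is inflated by 0.008699/0.008429 = 1.03, which cancels)
- 8% v 4%: 0.008989/0.008699 = 1.03
- 12% v 4%: 0.009302/0.008699 = 1.07
- 15% v 5%: 0.009554/0.008769 = 1.09

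In simulations of the same scenarios, censoring at last contact gave 1.00 within simulation error.

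**4. With discrete interviews.** If status is learned only at an interview around week 21, simulation gives 1.02, 1.05 and 1.07 for the three unequal scenarios. If every loss occurs before that interview, the ratio is 1.00, because there is no known event-free time to discard.

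**5. Against sampling error.** Expected events are 0.10×75 = 7.5 and 0.10×125 = 12.5. SE(log HR) ≈ √(1/7.5 + 1/12.5) = 0.46, and ln(1.09)/0.46 = 0.19, so the largest shift above is about a fifth of a standard error.

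No calculation was made for preterm delivery.

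**The case against.** The strongest reply is that 7.3 hands the treatment of these women to the SAP, which is not available here, and that endpoint-level censoring is ordinary SAP content. This explains part of the point but does not remove it. Section 8.1 does not leave the matter open: it states exclusion, and section 8 is what the SAP is to be built from. The two sections need to be reconciled.

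Two stronger readings are tempting, and the text does not support them.

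- A reader might infer that 8.1 defeats the right censoring in 8.3.2. It does not. That censoring is described for women no longer at risk, and it still operates among the women retained. Section 8.3.2 says nothing about censoring for loss.
- A reader might infer that Table 3's 75:125 is contradicted in a way that matters. The detectable relative risk moves only from 2.52 to 2.56, either side of the printed 2.55. Nor would keeping the women restore full information, since a censored woman contributes only part of the risk period.

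Other parts of the reply stand. The unequal loss rates are assumptions: the protocol gives one rate, 4%, and section 3.2.1 expects loss to be minimal. Censoring at last contact is unbiased here because loss was modeled as unrelated to outcome; if women who miscarry drop out more often, censoring is biased too. Lost and withdrawn women are reported descriptively in every report, so imbalance would be visible. Section 8.1 reaches only withdrawals before the outcome is known, and 7.3 treats women who decline further participation as having withdrawn consent, which may limit use of their data.

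**Conclusion.** The point holds as a low-severity one confined to two secondary endpoints. As written, 8.1 discards known event-free time and selects on later follow-up, and it settles a matter that 7.3 leaves to the SAP.

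At the planned 4% loss, equal across cohorts, there is no bias and about 3 and 5 women are dropped. With assumed unequal loss of 8% v 4% up to 15% v 5%, the spontaneous-abortion hazard ratio is inflated by about 2% to 9%, depending on how continuous contact is and when loss occurs. This rests on constant hazards and on loss independent of outcome. The size for preterm delivery is unknown. The documents do not support a claim that the planned analysis will be biased, only that it could be if retention differs. Exclusion for endpoints that need the birth outcome, including the primary endpoint, is not questioned here.

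**What to change.** Reconcile 8.1 with 7.3 and 8.3.2. Limit the exclusion to endpoints that need the birth outcome, such as structural defects, size at birth and growth. For spontaneous abortion and preterm delivery, include lost and early-withdrawn women from their gestational age at enrollment and censor them at the gestational age when last known to be pregnant. Use data from withdrawn women only as far as their consent allows. State in 8.3.2 that loss and withdrawal are censoring events, alongside no longer being at risk.

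The cost is a sentence or two, and the interviews already record the needed dates. The downsides are small: censoring assumes that loss is unrelated to outcome, which should be stated, and a woman with no contact after intake adds almost no time. Table 3 needs no change.
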